3.3.1.2. Exclusion Criteria

Candidates will be excluded from study entry if any of the following exclusion criteria exist at Screening or Baseline visits or at the timepoint specified in the individual criterion listed.

- Participant is receiving regularly scheduled RBC transfusion therapy (also termed chronic, prophylactic, or preventative transfusion).
- Participant is taking or has received crizanlizumab (ADAKVEO®) within 90 days prior to Screening.
- Participant weighs > 133 kg (292 lbs.).
- Participant has a significant active and poorly controlled (unstable) hepatic disorder clearly unrelated to SCD.
- Participant has any of the following laboratory values at Screening:
 - Absolute neutrophil count (ANC) < 1.0 × 10⁹/L
 - b. Platelet count < 80 × 10⁹/L
 - c. Hemoglobin < 4.0 g/dL for adults and < 5.0 g/dL for participants ages 12 to < 18 years of age

 - d. Estimated glomerular filtration rate (eGFR) < 30 mL/min using Chronic Kidney Disease-Epidemiology Collaboration (CKD-EPI) formula in adults, and Schwartz formula in adolescents.

NOTE: Laboratory assessments conducted during Screening may be done by the local laboratory and must include at least a CBC with total and differential leukocyte count, platelet count, and hemoglobin, a chemistry panel with creatinine, and a serum pregnancy test to assess participant eligibility. Laboratory assessments conducted during the index VOC admission that are obtained within 7 days prior to screening may be used for Screening assessments if done as part of standard medical care.

- Participant has known active (symptomatic) COVID infection or tests positive for COVID-19 at any time during their index admission.
- Participant has a history of unstable or deteriorating cardiac or pulmonary disease within 6 months prior to Screening including severe or unstable pulmonary hypertension.
- Participant has had treatment for a malignancy within the 12 months prior to Screening (except non-melanoma skin cancer and in situ cervical cancers).
- 9. Participant has had a stroke within the 2 years prior to the Screening Visit.

- 10. Participant has a positive test indicative of active malaria infection at Screening. Testing to be conducted at local laboratories in malaria-endemic regions at the discretion of the Investigator.
- Participant has any confirmed clinically significant drug allergy and/or known hypersensitivity to monoclonal antibody therapeutics or formulation components of the study drug or a related drug.
- 12. Participant has been treated with another investigational agent within 30 days or 5 half-lives of the investigational agent (whichever is greater) prior to Screening.
- 13. Participant has had a major surgery within 8 weeks prior to the Screening Visit.
- Participant is pregnant, breastfeeding, or planning to become pregnant during the 90-day treatment period.
- 15. Participant, parent, or legal guardian are unlikely to comply with the study procedures.
- 16. Participant has other medical, or psychological, or behavioral conditions that, in the opinion of the Investigator, would: confound or interfere with evaluation of safety, efficacy, and/or PK of the investigational drug; prevent compliance with the study protocol; preclude informed consent; or render the participant, parent, or caretaker unable/unlikely to comply with the study procedures.

3.3.2. Participant Completion

Participants not enrolling in the OLE study will complete the study at the time of the last scheduled study procedures at the Day 161 visit. For participants who enroll in the OLE study, the Day 91 visit will be the final study visit. Participants may receive their first dose in the OLE study on the same day as the completion of the study assessments for the Day 91 visit. Participants who terminate the study prior to the Day 91 visit will be requested to complete the assessments as outlined for the Early Termination (Day 91) Visit. Participants not enrolling in the OLE study that complete the Day 91 visit but terminate prior to the Day 161 visit will be requested to complete the assessments as outlined for the End of Study (EOS; Day 161) Visit. Participants who require further follow-up for an AE/serious adverse event (SAE) will be followed according to Section 7.9.

3.3.3. Study Discontinuation

The Sponsor has the right to terminate this study at any time. In any instance of early termination of the study, the Sponsor will notify, in writing, the Investigators, regulatory authorities and ethics committees (Institutional Review Board [IRB]/Ethics Committee [EC]) and will specify the reason(s) for termination.

3.3.3.1. Early Discontinuation of Individual Participants

Participants will be informed that they are free to withdraw from the study at any time and for any reason. The Investigator must withdraw from the study any participant who requests to be withdrawn. Participants who ask to leave the study early (withdraw consent) should be encouraged to undergo the tests and evaluations listed for the Early Termination (ET) Visit (ie, early termination is intended for participants who withdraw consent). If a participant

withdraws before completing the study, the date and reason for withdrawal is to be documented on the electronic case report form (eCRF).

Participants may discontinue the study for any of the following reasons:

- Adverse event
- Withdrawal of consent
- Discretion of the Investigator
- Participant is lost to follow-up
- Participant is noncompliant
- Pregnancy. Report the pregnancy according to the instructions in Section 7.4.

A participant that withdraws from the study or is lost to follow-up will not be replaced.

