6.2.1. Instructions for Female Participants of Childbearing Potential

For female participants of childbearing potential (post-menarchal) who are sexually active, pregnancy should be avoided by the use of a highly effective method of contraception (as outlined in Section 6.2.3) consistently throughout the study and for at least 165 days after dosing.

Female participants who become pregnant during the study will be withdrawn from the study. Pregnancy reporting requirements are outlined in Section 7.4.

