8.2. Determination of Sample Size

Up to 280 participants will be enrolled in the study. Participants will be randomized in a 1:1 ratio to receive treatment with a single dose of inclacumab or placebo.

The study uses a group sequential design to evaluate the primary efficacy endpoint based on 2 sequential analyses: (i) one interim analysis after a minimum of 75 participants per arm have completed the study through 90 days, and (ii) if required, a final study analysis based on approximately 140 participants per arm.

For the primary endpoint, the planned sample size of up to 280 participants (140 participants per treatment group) provides approximately 90% power to detect a targeted 50% relative reduction in the proportion of participants with at least 1 VOC that required admission to a healthcare facility and treatment with parenteral pain medication within 90 days from a rate of 35% for placebo to 17.5% for inclacumab, using a 2-sided test of the difference in 2 binomial proportions (Normal approximation). To maintain an overall Type I error rate of 0.05, calculations assumed an O'Brien-Fleming boundary of the Lan-DeMets alpha-spending function (East version 6.5). For the sample size calculation, a 5% drop-out rate during the 90-day study period was used.

With this sample size, the smallest observed treatment difference expected to be statistically significant at the final analysis is approximately a 32% relative reduction (ie, reduction in the proportion of participants with at least 1 VOC that required admission to a healthcare facility and treatment with parenteral pain medication within 90 days of randomization from 35% for placebo to 23.8% for inclacumab).

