9.3. Quality Control and Quality Assurance

9.3.1. Monitoring

Site personnel will be provided with training on how to collect quality data for the study, and a Sponsor monitor or designee will be contacting the site periodically to review study conduct and data recorded at the site. At the Sponsor's discretion, onsite monitoring visits may be conducted pre-study, during the study, and following study completion. These visits are to provide the Sponsor with the opportunity to evaluate study progress; verify the accuracy and completeness of source data and eCRFs; and ensure that all protocol and Good Clinical Practice (GCP) requirements, applicable country-specific regulations, and Investigator obligations are being fulfilled. The Sponsor may terminate study participation if study site personnel do not follow the protocol or GCP requirements. Additionally, individual participants may be excluded if a medical record review indicates protocol violations or if other factors appear to jeopardize the validity of the study.

The Investigator agrees to cooperate with the monitor to ensure that any problems detected during the monitoring visits are resolved.

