5.3.1. Primary Efficacy Endpoint

For the primary efficacy endpoint, VOCs that meet the protocol-specified definition as assessed by the VOC Adjudication Committee with an onset date from randomization (Day 1) through the 90-day study period (Day 91), inclusive, will be used in the analysis.

The proportion of participants with at least 1 VOC that required admission to a healthcare facility and treatment with parenteral pain medication within 90 days (primary endpoint) from randomization will be compared between treatment groups using the exact Cochran-Mantel-Haenszel (CMH) general association test, stratified by the randomization stratification factors (baseline HU use [yes; no] and number of VOCs in the 12 months prior to study entry [2 to 4 episodes; 5 to 10 episodes]).

Every effort will be made to obtain the 90-day re-admission status for a VOC for each participant. For purposes of the primary analysis, participants with an unknown 90-day readmission status (e.g., participants who discontinue the study prior to 90 days and without a readmission for a VOC) will be classified as having experienced at least 1 protocol-defined VOC within 90 days (i.e., counted as "failure"). A sensitivity analyses based on observed data (i.e., without imputation of re-admission for early study discontinuation) will be performed to assess the robustness of the primary analysis results to assumptions regarding drop-outs.

SAS code for the exact CMH test similar to the following will be used for the primary analysis (where trtgrp is the randomized treatment group and response is an indicator variable for occurrence of at least one protocol-defined VOCs during the 90 days post randomization):

```
PROC LOGISTIC;
CLASS trtgrp /PARAM=REF;
MODEL response (event='Yes') = trtgrp;
STRATA = <categorical variables>;
EXACT trtgrp;
RUN;
```

Similarly, the proportion for each treatment group and the difference in proportions between treatment groups (inclacumab versus placebo) will be estimated by the weighted average of the observed proportions and the differences in observed proportions over the strata using the CMH weights and 95% confidence intervals (CIs) provided (Mehrotra and Railkar 2000).

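### Participants may leave this single-dose trial for reasons other than withdrawn consent; VOC recording then stops, and an event-free participant with unknown 90-day status is counted as a failure

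*Protocol*

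**What the plan says.** The only dose is given on Day 1, the day of randomization (SAP 2.4). Five places then govern what happens to the primary outcome of someone who leaves early.

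- **Protocol 3.3.3.1** opens its list with "Participants may discontinue the study for any of the following reasons". The list covers adverse event, withdrawn consent, investigator discretion, loss to follow-up, non-compliance and pregnancy. A parenthesis in the same section says "early termination is intended for participants who withdraw consent".
- **Protocol 6.2.1** is mandatory: "Female participants who become pregnant during the study will be withdrawn from the study".
- **Protocol 4.6** goes the other way for a permanently stopped infusion. That participant stays in the study through Day 161.
- **Protocol 7.6.1** records VOCs to Day 91, or to Day 161 for those not entering the extension, but stops earlier if the participant discontinues the study.
- **SAP 5.3.1** treats an unknown 90-day status as a failure and gives early leavers as its example: "participants who discontinue the study prior to 90 days and without a readmission for a VOC) will be classified as having experienced" a protocol-defined VOC. It also promises efforts to obtain the status and one sensitivity analysis on observed data.

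**The concern.** Once the infusion is over there is no further study treatment to stop, so exit mainly ends observation. The primary outcome is a yes/no status at 90 days. It could often still be learned by telephone or from records for a participant who stops visits but agrees to contact. The protocol closes VOC recording instead, and the SAP fills the gap with an event.

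If such exits are equally common in both arms, the added events shrink the difference. If exits for adverse events or at investigator discretion differ by arm, they shift the comparison in a direction unrelated to VOCs. Time to first VOC (SAP 5.3.2.1) censors the same people at their end of study, so one participant can be a failure on the primary endpoint and event-free on the first secondary endpoint.

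**Working it through.** **Inputs.** Protocol 8.2 gives 35% versus 17.5%, 140 per arm, 5% drop-out, "using a 2-sided test of the difference in 2 binomial proportions (Normal approximation"), and an O'Brien-Fleming-type Lan-DeMets boundary with an interim at 75 per arm. SAP 2.1 says about 26% of 280 were randomized: 0.26 × 280 = 72.8, or about 36.4 per arm.

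**Reproducing the plan.** With z the two-sided critical value, p̄ the mean of the two rates and Δ their difference,

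SE0 = √[2p̄(1−p̄)/n], SE1 = √[(p1(1−p1)+p2(1−p2))/n], power = Φ[(Δ − z·SE0)/SE1].

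- The spending function at 75/140 leaves a final two-sided level of 0.0471 (z = 1.985).
- Removing 5% drop-out leaves 0.95 × 140 = 133 per arm. Final-look power is then 90.0%, or 90.2% counting both looks. This matches the stated figure: the sample size "provides approximately 90% power to detect a targeted 50% relative reduction".
- The plan's calculation therefore treats drop-outs as lost sample size, whereas the primary analysis counts those with unknown status as events.

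**Failure imputation.** Let d be the share of an arm with unknown status, unrelated to the outcome they would have had. The analysed rate is p + (1−p)d. At d = 5%:

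- placebo: 0.35 + 0.65 × 0.05 = 38.3%
- inclacumab: 0.175 + 0.825 × 0.05 = 21.6%
- difference: 17.5 points becomes 16.6 points

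**Power, equal d in both arms:**

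| d | 140 per arm, level 0.0471 | 36.5 per arm, level 0.05 |
|---|---|---|
| 0 | 91.5% | 39.5% |
| 2.5% (half of the 5% recovered) | 88.7% | 36.5% |
| 3.75% (a quarter recovered) | 87.3% | 35.2% |
| 4.5% (a tenth recovered) | 86.4% | 34.4% |
| 5% (none recovered) | 85.8% | 33.9% |

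Worked line for 140 per arm, d = 5%: SE0 = 0.0547 and SE1 = 0.0538, so (0.16625 − 1.985 × 0.0547)/0.0538 = 1.07 and Φ(1.07) = 85.8%. A two-look calculation gives 91.6% falling to 86.0%.

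**One case at about 36 per arm.** An imputed failure adds 1/36 = 2.8 points gross. Some leavers would have had an event anyway, so the expected net shift is 0.65/36 = 1.8 points on placebo and 0.825/36 = 2.3 points on inclacumab. These use the full 90-day event rates. For someone who leaves event-free late in the period, the shift is nearer 2.8.

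**Unequal exits (assumed values).** With d = 2.5% on placebo and 7.5% on inclacumab, two-look power at 140 per arm is 65.1%. With 10% and 5% it is 94.9%, so the distortion can favour either arm. With no drug effect and a 35% rate in both arms, a 5-point gap in d creates a false difference of 0.65 × 5 = 3.25 points.

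**The case against.** Several stronger readings are tempting, and the documents do not support them.

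- **Exit ends all follow-up.** It does not. AE/SAE follow-up continues (Protocol 5.9, 7.8) and pregnancy is followed to outcome (7.4). An Early Termination visit is requested, and its schedule column includes VOC assessment. That visit gives status only up to exit, however.
- **Every imputed case is a false failure.** Some leavers would have been readmitted; the net shifts above allow for that.
- **The whole power loss comes from these exits.** The 5% is total drop-out, including withdrawn consent and loss to follow-up, which continued contact cannot recover. No breakdown by reason or arm is given.
- **Leaving serves no purpose.** Protocol 6.1.2 restricts several therapies during the study, so leaving has consequences beyond study drug.
- **Monitoring exclusions also end follow-up.** Protocol 9.3.1 says "individual participants may be excluded if a medical record review indicates protocol violations" but does not define exclusion, and SAP 5.3 analyses all randomized participants regardless of adherence.

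It can also be argued that the parenthesis on withdrawn consent describes the Early Termination visit rather than limiting the grounds for exit. That reading is possible, and it is a reason to clarify the text. The SAP imputes only when status is unknown, so a status actually obtained should already count. That is fair, but 7.6.1 stops the recording and no route for later collection is given. The observed-data sensitivity analysis helps, but it assumes that exit carries no information about outcome, which is doubtful for exits driven by adverse events or discretion.

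Finally, the trial stopped at about 26% enrolment and power is about 39% even with complete data. This point cannot rescue interpretability. It concerns avoidable missing data and bias in a small comparison.

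**Conclusion.** The concern holds in a limited form. Followed as written, the plan stops collecting a primary outcome that may still be obtainable and replaces it with an event. With equal exits, the loss of power is at most 5.7 points at 140 per arm (91.5% to 85.8%) and 5.6 points at 36 to 37 per arm (39.5% to 33.9%), taking the protocol's 5% drop-out and imputing all of it. The avoidable part is smaller: if 10% to 50% were recoverable, the gain is about 0.6 to 2.9 points and 0.5 to 2.6 points respectively. That recoverable share is an assumption. Unequal exits could matter more, but the documents give no counts by arm or reason, so those figures show sensitivity only. The documents do not settle which grounds for leaving the study are right, and this point takes no position on that.

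**What to change.** 1. Reconcile Protocol 3.3.3.1, 4.6, 6.2.1 and 7.6.1 on who leaves the study and when VOC recording ends.
2. For participants who stop visits without withdrawing consent to contact, keep the VOC-status contacts already scheduled for Days 31, 61 and 91, or check records instead. Record and adjudicate VOCs through Day 91.
3. In SAP 5.3.1, state that VOC status obtained after discontinuation is used, and that failure is imputed only when status is still unknown. This fits SAP 5.3, which already includes everyone regardless of adherence.

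The cost is a protocol clarification, a few extra contacts and some analysis wording. Given the early stop, the benefit is limited to participants not yet past Day 91.

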3.3.4. Lost to Follow-up

Participants who do not return for a scheduled visit, as defined by the visit schedule, and cannot be reached to determine the reason for the missed visit, may be considered lost to follow-up. The site will attempt to contact the participant through a minimum of 2 telephone calls. If the participant still cannot be contacted, the site will send a certified letter to the last known address of the participant. If no contact is made by the participant, the site will consider the participant lost to follow-up. All follow-up attempts will be documented and kept with the participant's source documentation, and the applicable eCRFs will be completed.

3.4. Study Duration

The total study duration for each participant will be variable based on the time from the start of the index VOC admission to Day 1. For example, if a participant begins screening at the start of a 10-day index VOC admission and is randomized the day of their index VOC resolution, the study duration would be 170 days, including a 10-day Screening period, a 90-day treatment period, and a 70-day (10 week) follow-up period.

Participants who enroll in the OLE study after Day 91 will have a total study duration of 91 days plus the length of their Screening period.

3.5. Treatments

Study drug will be provided to the study sites in a blinded fashion as a solution for IV infusion. All study drug will be administered at the clinical study site. Participants will be randomized into one of 2 treatment groups: inclacumab or placebo. The active inclacumab and placebo solutions will look identical to maintain the blind. The Investigator, site staff, participant, and Sponsor study personnel (or their designees) will be blinded to the study group to which the participant is randomized. Participants will be dosed as follows:

- Inclacumab: 30 mg/kg inclacumab administered IV on Day 1
- Placebo: placebo administered IV on Day 1

4. STUDY DRUG INFORMATION

4.1. Description of Active Study Drug – Inclacumab

The inclacumab drug substance is manufactured by fermentation cell culture using Chinese hamster ovary (CHO) cells followed by purification. The drug substance and drug product are manufactured in accordance with Good Manufacturing Practice (GMP).

Inclacumab drug product is a sterile, clear to opalescent liquid concentrate for infusion with an approximate pH of 5.5 provided in colorless, 10 mL single-use vials. Each vial contains 500 mg of inclacumab and the following excipients:

4.2. Description of Placebo for Inclacumab

The placebo for inclacumab to be used in this study will be a matched placebo for IV infusion with the same excipients found in inclacumab without the active product.

4.3. Packaging and Labeling

The study drug will be packaged and labeled in a manner consistent with the study design.

Vials of study drug will be labeled according to applicable regulations for an investigational drug.

If the packaging is damaged, or if there is anything unusual about the appearance or attributes of the vials or study drug, do not use the study drug. The vial in question should be saved at the study site and the problem immediately reported to the Sponsor, or designee per the Pharmacy Manual (provided separately).

4.4. Storage and Handling

The inclacumab and placebo vials are to be stored at 2° to 8°C (36 to 46°F) prior to dilution in a monitored, locked refrigerator with limited access. Detailed instructions for storage and handling of study drug after dilution are provided in the Pharmacy Manual.

Study drug must be stored in a secure location and should not be used after the expiration, expiry, or use-by date.

The study drug will be provided by the Sponsor in 10-mL single-use vials that should be protected from light.

4.5. Instructions for Use and Administration

Detailed instructions for preparation and administration of study drug can be found in the Pharmacy Manual.

4.6. Management of Infusion-Related Reactions (IRR)

Participants will be monitored throughout the infusion and for 60 minutes after completion of study drug infusion for adverse reactions. If an infusion-related reaction (IRR) or hypersensitivity reaction of Grade 3 or higher (Appendix 4) occurs during study drug administration, the infusion should be paused, and the participant should be treated for the

reaction per site standard operating procedures as indicated. The participant will be monitored for resolution of the infusion or hypersensitivity reaction. If the reaction resolves to Grade 1 or less, study drug infusion may be reinitiated. Specific instructions for re-initiation of infusion are provided in the Pharmacy Manual. If the reaction recurs at a level of Grade 3 or higher, study drug administration should be permanently discontinued. Exact times of infusion stop and start must be recorded.

All IRRs will be recorded as an adverse event of special interest (AESI, Section 7.3) or SAE (if serious criterion is met; Section 7.1.2). If the study drug infusion is permanently discontinued, the participant should continue in the study to complete all safety, PK, and PD assessments through Day 161. However, the participant will be ineligible for the OLE study.

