7.2.3. Abnormal Laboratory Values

Clinically significant laboratory abnormalities will be recorded in the AE eCRF (eg, abnormalities that have clinical sequelae, more frequent follow-up assessments, or further diagnostic investigation). If the clinically significant laboratory abnormality is a sign of a disease or syndrome (eg, alkaline phosphatase and bilirubin 5 × upper limit of normal [ULN] associated with cholecystitis), only the diagnosis (eg, cholecystitis) needs to be recorded in the eCRF.

If the clinically significant laboratory abnormality is not a sign of a disease or syndrome, the abnormality itself should be recorded on the eCRF. If the laboratory abnormality can be characterized by a precise clinical term, the clinical term should be recorded. For example, an elevated serum potassium level of 7.0 mEq/L should be recorded as "hyperkalemia".

Observations of the same clinically significant laboratory abnormality from visit to visit should not be repeatedly recorded on the AE eCRF, unless their severity, seriousness, or etiology changes.

7.3. Adverse Events of Special Interest, Serious Adverse Events, Serious Adverse Drug Reactions, and Requirements for Immediate Reporting

Any biologic agent administered IV may have the potential to cause infusion-related reactions (IRR; see Investigator's Brochure). In this study, IRRs should be reported as adverse events of special interest (AESI). Signs or symptoms of IRRs may include chills/rigors, myalgias, headache, rash, fatigue, nausea, vomiting, dyspnea, and/or hypotension. Shock may occur during or shortly after infusion and usually occurs during and/or up to 24 hours after the first infusion.

All AESIs or SAEs, regardless of causal attribution, must be reported by the Investigator or designee or site personnel within 24 hours of AESI or SAE awareness. The AESI or SAE will be reported by completing the SAE eCRF. AESIs will be recorded on the SAE eCRF within 24 hours of the site's awareness of them, even if they do not meet criteria for an SAE.

The Sponsor or designee may request additional source documentation pertaining to the AESI or SAE from the investigational site. Follow-up reports must be submitted within 24 hours of awareness, and participant identifier information (eg, name, medical record number) must be redacted in the hospital discharge summaries, autopsy reports, and/or death certificates.

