APPENDIX 4. INFUSION-RELATED REACTION GRADING

The severity of infusion-related reactions (IRRs) will be graded using the National Cancer Institute Common Terminology Criteria for Adverse Events (NCI-CTCAE), Version 5.0 per Table 4, below. The CTCAE quick reference guide can be found at the Cancer Therapy Evaluation Program CTCAE website (CTCAE Website).

Table 4: Infusion-related Reactions

| Grade 1 | Mild transient reaction; infusion interruption not indicated; intervention not indicated |
|---------|--------------------------------------------------------------------------------------------------------------------------------------------------------------------------------------------------------------|
| Grade 2 | Therapy of infusion interruption indicated but responds promptly to symptomatic treatment (eg, antihistamines, NSAIDs, narcotics, IV fluids); prophylactic medications indicated for ≤ 24 hours |
| Grade 3 | Prolonged (eg, not rapidly responsive to symptomatic medication and/or brief interruption of infusion); recurrence of symptoms following initial improvement hospitalization indicated for clinical sequelae |
| Grade 4 | Life-threatening consequences; urgent intervention indicated |
| Grade 5 | Death |

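### Protocol Section 4.6 treats a Grade 4 infusion reaction like Grade 3, so this protocol sets no mandatory bar to re-exposure when the infusion is completed or the reaction starts after it ends

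*Protocol*

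**What the plan says.** Protocol Section 4.6 sets the trigger: if an infusion-related or hypersensitivity "reaction of Grade 3 or higher (Appendix 4) occurs during study drug administration, the infusion should be paused". On restart it says "If the reaction resolves to Grade 1 or less, study drug infusion may be reinitiated", and adds that "Specific instructions for re-initiation of infusion are provided in the Pharmacy Manual". On stopping it says "If the reaction recurs at a level of Grade 3 or higher, study drug administration should be permanently discontinued".

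A participant whose infusion is permanently discontinued stays in the study for follow-up, and the section then adds "However, the participant will be ineligible for the OLE study". On observation it says "Participants will be monitored throughout the infusion and for 60 minutes after completion of study drug infusion for adverse reactions".

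Appendix 4, Table 4, describes a Grade 4 reaction as "Life-threatening consequences; urgent intervention indicated". Section 7.3 makes every infusion-related reaction an adverse event of special interest (AESI). In general wording about intravenous biologics it warns that "Shock may occur during or shortly after infusion and usually occurs during and/or up to 24 hours after the first infusion".

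Sections 3.1 and 6.3 place the first OLE dose at the Day 91 visit, under a separate protocol, for participants who meet that study's eligibility requirements. This protocol does not list those requirements.

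**The concern.** The OLE bar in Section 4.6 depends on whether the infusion was stopped, not on how severe the reaction was. A participant whose Grade 3 reaction recurs is barred. A participant who had a life-threatening reaction, recovered and completed the infusion is not, and neither is one whose life-threatening reaction began after the infusion ended. Exclusion criterion 11 keeps people with known hypersensitivity to monoclonal antibodies or to the formulation out of this study. The protocol states no equivalent bar for someone who shows such a reaction to the study infusion itself.

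What is at stake is participant safety on the trial's only AESI. Re-exposure could happen by restarting the Day 1 infusion or by giving the first OLE dose at Day 91.

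**Working it through.** The main check is of the text, and the only arithmetic is a ceiling on reach. I took the Section 4.6 rules, graded reactions by Appendix 4, and followed each course that a Grade 4 reaction could take.

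| Course of a Grade 4 reaction | Permanent stop under 4.6? | OLE bar in this protocol? |
|---|---|---|
| During infusion, restarted, recurs at Grade 3 or higher | Mandatory | Yes |
| During infusion, not restarted (unresolved, or investigator's choice) | Infusion has in effect been stopped for good | Yes |
| During infusion, resolves to Grade 1 or less, restarted and completed | None required | None stated |
| Begins after the infusion has ended | Nothing left to stop | None stated |

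The first two rows are covered. The last two are open. The third depends on the restart rule. The fourth does not, because the OLE bar can only be triggered by discontinuing an infusion that is still running.

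I then looked for any other provision that would close the last two rows:

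- Section 7.2.1 lets the investigator stop study treatment after any adverse event. It is optional, and after a completed single infusion there is no treatment left to stop.
- Section 3.3.3.1 lists an adverse event and investigator discretion among the reasons for leaving the study. Section 6.3 offers the OLE to participants who complete the study, so this gives a route to keep someone out. It is also optional.
- Section 5.3.3 says participants should be well, with stable vital signs and no sign of a reaction, before release from observation. This covers observation after dosing. It does not govern later dosing.
- Section 7.3 requires AESI and serious adverse event (SAE) reports within 24 hours. Sections 3.1 and 7.7 provide unblinded DMC review, with ad hoc meetings possible. These make the event known but prescribe no consequence for OLE entry.
- The SAP contains no stopping rule for infusion reactions and no OLE eligibility rule.

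Reach: SAP Section 2.1 puts randomization at about 26% of the planned 280.

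- 0.26 × 280 = 72.8, or about 73 participants.
- 72.8 / 2 = 36.4, or about 36 per arm.

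So at most about 73 OLE first doses could fall under this rule, if every randomized participant qualified for the OLE and chose it. This is a loose ceiling, because the people affected are only those with a Grade 4 reaction in one of the two open rows. The documents give no Grade 4 rate. Section 1.3.2 reports more than 700 earlier exposures and describes 20 mg/kg every 4 weeks in 188 patients as well tolerated, but it gives no count by grade. No frequency can be calculated.

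**The case against.** The strongest reply is that the outcome depends on documents not available here. Restart instructions are in the Pharmacy Manual, and OLE eligibility is in another protocol. A parent protocol need not list every exclusion of its extension. A reader might infer from Section 4.6 that participants with Grade 4 reactions will be admitted to the OLE. The documents do not support that. They show only that this protocol does not forbid it.

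A reader might also set the 24 hours in Section 7.3 against the 60 minutes in Section 4.6 and infer that most of the risk falls outside observation. That does not follow either. Section 7.3 speaks of intravenous biologics in general and gives no distribution of onset over the period, so elapsed time cannot stand in for risk. Section 5.3.3 also makes release conditional on freedom from symptoms. A reaction that starts after release would still be missed, but its likelihood cannot be stated.

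Third, restart is permitted and not required. The section is coherent as it stands: treat, wait for near-resolution, stop on recurrence. Every Grade 4 reaction would be reported long before Day 91. These points reduce the chance of harm. They do not supply a rule, since each leaves the decision after a life-threatening reaction to individual judgement.

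Finally, the sponsor decided in June 2023 to stop before full enrollment, and dosing is a single infusion on the day of randomization. A new stop rule would therefore probably change no infusion in this trial. That stands, and it moves the practical weight to any OLE doses still to be given.

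**Conclusion.** The concern holds as a gap in this protocol. Grade 4 is handled exactly like Grade 3, and no mandatory bar to re-exposure applies to a participant who completes the infusion after a Grade 4 reaction or who reacts after it ends. Existing safeguards reduce the risk without setting a bar.

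The size is limited. The event is likely to be rare, but no rate can be given. The ceiling is about 73 OLE first doses, and the documents do not say how many Day 91 visits remain. No efficacy result or planned inference is affected.

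The conclusion rests on the text of this protocol and SAP alone. If the OLE protocol already excludes participants with Grade 4 reactions, the OLE part of the gap is closed in practice. If the Pharmacy Manual already forbids restart after Grade 4, the restart part is closed too.

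**What to change.** Amend Section 4.6 in three respects:

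- Limit pause-and-restart to Grade 3 reactions.
- Require permanent discontinuation after any Grade 4 reaction.
- Make any Grade 4 infusion-related or hypersensitivity reaction, during or after the infusion, a bar to OLE entry whether or not the infusion was completed.

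Because enrollment has stopped, two checks come first. Review the blinded AESI and SAE reports for Grade 4 reactions before any remaining Day 91 OLE dose. Confirm that the OLE protocol carries the same stop rule and eligibility bar. If both are clear, amending this protocol adds little.

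The checks need no unblinding, no amendment to this protocol and no statistical change. The amendment is short, but Section 9.4.4 requires ethics and regulatory approval before it takes effect, and Section 3.3 plans about 60 sites. The primary analysis would not suffer: participants whose infusion is stopped stay in follow-up (Section 4.6), and SAP Section 5.3 analyses everyone randomized.

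The main downside is that a placebo participant with a Grade 4 reaction would also lose OLE access. That loss is modest, because Section 4.2 gives placebo the same excipients as inclacumab, so a true reaction to placebo would be to components also present in the active product.
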